Allocation concealment: The RT will be blinded as to whether the subject receives a dose of IM epinephrine. Once a patient is determined to be eligible for the study, the research team will complete informed consent/assent. A pharmacy generated randomization schedule will be utilized and sealed envelopes with the allocations (treatment or control) will be kept in the charge nurse's office.

At the time of allocation, the charge nurse will instruct all staff to leave the subject's room. The charge nurse will then open the designated envelope and personally prepare and administer IM epinephrine if the subject is allocated to the treatment arm. If the subject is allocated to the control arm, the charge nurse will draw up a syringe with the appropriate amount of saline as if an injection of epinephrine was going to be given to the participant. The charge nurse will take this syringe into the subject's room, but not administer it. Instead, a 'sham' Band-Aid will be placed over the thigh of the subject. They will be instructed not to reveal to the RT, research team, or bedside nurse whether or not an injection was actually given. Participants and families will be similarly instructed. The RT will remain blinded throughout and will be responsible for measuring all PEFRs and CASs.

Having block sizes that are randomly determined, as well as having larger block sizes of 8-12 will help minimize a member of the research team or the RT guessing the allocation of the next participant and potentially biasing recruitment or assessment. To further assess blinding, at the conclusion of the study, we will ask the RTs to guess which group the subjects they assessed were in.

Study data: The following data will be measured at time points (t_{15} , t_{30} , t_{60} , t_{90} , and t_{120}) minutes following IM epinephrine or sham drug administration: PEFR (if able), CAS, heart rate, respiratory rate, and pulse oximetry. This data will also be recorded at the time of discharge or admission from the ED. Also recorded will be amount and timing of bronchodilator, anticholinergic, and corticosteroid therapy given. Additionally, any other therapies and interventions will be recorded (i.e. oxygen administration, assisted ventilation, magnesium sulfate administration, etc.). ED length of stay as well as disposition will be noted.

Primary outcome measure: Change in percent of predicted PEFR/CAS 15 minutes after the study intervention (t_{15}).

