Secondary outcome measures:

1. Change in percent of predicted PEFR/CAS at t₁₅

- 2. Disposition
- 3. Change in percent of predicted PEFR/CAS at t₃₀, t₆₀, t₉₀ and t₁₂₀
- 4. Change in percent of predicted PEFR/CAS at t₃₀, t₆₀, t₉₀ and t₁₂₀
- 5. Change in respiratory rate at t_{15} , t_{30} , t_{60} , t_{90} and t_{120}
- 6. Change in heart rate at t_{15} , t_{30} , t_{60} , t_{90} and t_{120}
- 7. Need for supplemental oxygen at t_{60} , t_{90} and t_{120} (defined as a room air pulse oximetry of <93%)
- 8. Need for albuterol at t_{60} , t_{90} and t_{120}
- 9. Number of hours of albuterol therapy
- 10. ED length of stay

Statistical analysis plan: First straightforward tests for differences among the two groups of individuals will be performed. Analysis of Variance (ANOVA) techniques will be used to test for differences among continuous variables, while Kruskal-Wallis, Fischer's Exact Tests and Wilcoxon methods will be used to test for differences among categorical variables. To examine the outcomes of: (1) change in percent of predicted PEFR/CAS, (2) respiratory rate, (3) heart rate, (4) hours of albuterol therapy and (5) length of stay in the ED, separate mixed-effects general linear models will be developed for each outcome (five models will be developed). The two arms (IM epinephrine and no epinephrine) will be analyzed as fixed effects, and time (time since randomization) will be analyzed as a repeated measures effect. Traditional risk factors (e.g. age, gender, and ethnicity) will be incorporated as covariates during secondary analyses. All main effects and all two-way interaction effects will be investigated for significance from the mixed-effects models developed. Negative binomial regression and logistic regression techniques will also be used to evaluate (7) need for supplemental oxygen and (8) need for albuterol. Life table analysis and Kaplan-Meier techniques will initially be used to analyze the time-related variables (e.g., time to discharge). The Log-rank test will be used to test for differences among survival curves. In addition, Cox (proportional hazards) regression techniques will be developed to test for differences among groups as well as allow for adjustment for additional covariates and risk factors. Cox regression will allow us to investigate all potential main effects and interaction effects. All statistical analyses will be performed by a statistician who is blinded to the treatment allocation of the two groups.

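### The claimed 80% Cox power at a hazard ratio of 1.82 needs about 88 events, and 54 children can supply at most 54; admitted children also need a stated rule in the time-to-discharge analysis

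*Combined protocol and SAP*

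**What the plan says.** **Power calculation.** Cox models will relate group assignment to time-related outcomes. With 54 analysable children (60 recruited, under 10% expected to drop out), the section claims 80% power for a hazard ratio of 1.82 at two-sided 0.05. It gives no number of events. The paragraph, which also covers the mixed and logistic models, ends by calling the numbers in each group more than enough.

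**Statistical analysis plan, time-to-event part.** "Life table analysis and Kaplan-Meier techniques will initially be used to analyze the time-related variables (e.g., time to discharge". Then: "The Log-rank test will be used to test for differences among survival curves". Cox regression is added for covariate adjustment. The event, the time origin and the handling of admitted children are not stated. The Study data section foresees both ways of leaving: "This data will also be recorded at the time of discharge or admission from the ED". It adds: "ED length of stay as well as disposition will be noted".

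**Statistical analysis plan, mixed models.** The list of five modelled outcomes ends with "4) hours of albuterol therapy and (5) length of stay in the ED, separate mixed-effects general linear models will be developed for each outcome". For these models, "time (time since randomization) will be analyzed as a repeated measures effect". As a first step, "Analysis of Variance (ANOVA) techniques will be used to test for differences among continuous variables".

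**The concern.** The power of a log-rank or Cox comparison depends on the number of events, not the number enrolled. A child leaves the emergency department once, so 54 children can give no more than 54 events. If the stated power cannot be reached even at that ceiling, a non-significant Cox result will look like better evidence of no effect than it is.

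The second issue is the Kaplan-Meier display. A child who has been admitted can no longer be discharged home from the department. Censoring that child treats later discharge home as still possible, so the curve estimates the proportion going home in a setting where nobody is admitted. In children enrolled for severe asthma, that could be far from the observed proportion.

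The third issue is wording. Hours of albuterol and emergency department length of stay have one value per child. The Study data section does not list them among the measurements at 15 to 120 minutes, so a repeated-measures time effect cannot be estimated for them.

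**Working it through.** **1. Cox power**

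Inputs from the Intervention and Power calculation sections: 1:1 allocation, hazard ratio 1.82, 80% power, two-sided 0.05, 54 children. ln(1.82) = 0.5988.

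Events needed:
- Schoenfeld: 4 × (1.960 + 0.842)² / 0.5988² = 87.5, so 88.
- Freedman: (1.960 + 0.842)² × (2.82/0.82)² = 92.8, so 93.

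Power if all 54 children have the event:
- Schoenfeld: Φ(0.5988 × √54 / 2 − 1.960) = Φ(0.240) = 59.5%.
- Freedman: Φ(√54 × 0.82/2.82 − 1.960) = Φ(0.177) = 57.0%.
- Simulated log-rank (27 per arm, exponential times, no censoring, 20,000 trials): 57.0%.

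Hazard ratio detectable at 80% power with 54 events: exp(2 × 2.802 / √54) = 2.14 (Schoenfeld); Freedman gives 2.23.

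Attempts to reproduce the plan's 80% (Schoenfeld):

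| Reading | Power |
|---|---|
| 54 events, two-sided (as stated) | 59.5% |
| 54 events, one-sided | 71.1% |
| 60 events, two-sided | 64.0% |
| 54 per arm, 108 events | 87.5% |
| Covariate with SD 1 in place of a 1:1 arm, 54 events | 99.3% |

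None gives 80%.

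If only discharge home is the event, the count falls. The documents give no discharge rate, so the shares below are assumptions:

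| Assumed share of 54 going home | Events | Power at 1.82 |
|---|---|---|
| 40% | 21.6 | 28.5% |
| about 52% | 28 | 35.4% |
| 65% | 35.1 | 42.6% |
| 80% | 43.2 | 50.3% |

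At 28 events the detectable hazard ratio is exp(2 × 2.802 / √28) = 2.88.

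**2. Kaplan-Meier with admitted children censored**

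All rates and times here are assumed. Times are lognormal with log-SD 0.35. Let p be the share going home, and F_h and F_a the distributions of time to home and time to admission.
- True proportion home by 6 h: p × F_h(6). For p = 0.40 and a 4 h median: 0.40 × Φ(ln(6/4)/0.35) = 0.40 × 0.877 = 0.351.
- What one minus Kaplan-Meier estimates: 1 − exp(−∫ p dF_h / [1 − p F_h − (1 − p) F_a]), integrated numerically from 0 to 6 h.

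| Share home, control v epinephrine | Median to home / admission | Kaplan-Meier shows | True |
|---|---|---|---|
| 40% v 65% | 4 h / 3 h | 74% v 83% | 35% v 57% |
| 40% v 65% | 4 h / 4 h | 57% v 74% | 35% v 57% |
| 40% v 65% | 3.5 h / 5 h | 46% v 70% | 38% v 61% |
| 50% v 60% | 4 h / 3 h | 78% v 81% | 44% v 53% |

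The size varies widely; the direction is upward in every case.

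**3. One value per child**

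A random-intercept model with one row per child was fitted to 500 simulated null trials (27 per arm, lognormal, log-SD 0.5). The standard error of the arm effect, taken from total variance, was 1.000 times the least-squares value, and both rejected in 3.6%. The restricted log-likelihood was unchanged (−51.848) whatever share of the variance was assigned to the child. The split is not identified, but the arm comparison is unaffected.

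**The case against.** **Weight.** These analyses are secondary. The primary outcome is the change at 15 minutes. Time to discharge is only an example and is not one of the ten numbered secondary outcomes, while disposition and length of stay are listed. The section first presents the sample of 54 with a mixed-model claim of 81% power, and its closing sentence covers three model types. All of this stands. A reader might infer that the trial's size was derived from the Cox figure; the documents do not say so. The Cox claim is nevertheless specific, and it is wrong.

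**Log-rank and Cox censored at admission are legitimate.** This stands. Under that coding they compare the cause-specific hazard of discharge home. Only the Kaplan-Meier display needs replacing. Naming discharge and admission separately in the Study data section also favours reading discharge as going home, though no definition is given.

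**Any exit as the event.** A reader might infer that this coding would point against an effective drug. In the 40% v 65% scenario with 4 h to home and 3 h to admission, the simulated log-rank did lean that way (mean z −0.64). But children on epinephrine then really do stay longer, by 0.25 × (4 − 3) h × exp(0.35²/2) = 0.27 h on average, so the test correctly describes time in the department. At 4 h and 4 h the mean z is 0.00, and at 3.5 h and 5 h it is +0.78. The documents give no such times, and the plan does not say that any-exit time would be read as efficacy.

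**Repeated-measures wording.** A reader might infer that two outcomes have no usable analysis or that false positives increase. Neither follows: the first-step ANOVA compares each once per child, and the arm estimate and standard error are the same.

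**Conclusion.** The Cox power statement is wrong as written. This needs no assumed admission rate, because one event per child caps the count at 54 analysed (60 recruited) against about 88 needed. At the ceiling, power is about 59.5% (57% by Freedman or simulation), not 80%. The calculation assumes 1:1 allocation and proportional hazards. Figures below the ceiling, such as 35% at 28 events, are illustrations.

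The secondary point holds conditionally: if the event is discharge home and admissions are censored, Kaplan-Meier overstates the proportion going home. The direction follows from the method; the amount cannot be fixed from the documents. The missing event definition and rule for admissions are real gaps, but they do not make the planned log-rank or Cox test invalid.

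The repeated-measures wording is a minor specification slip with no effect on the arm comparison.

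**What to change.** 1. **Power calculation.** Restate the Cox power by expected number of events under a stated event definition, giving the assumed discharge rate if only discharge home counts. Drop the claim of ample numbers as regards the Cox analysis. Cost: a less favourable figure.

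2. **Statistical analysis plan, time to discharge.** State the event and the time origin. If the event is discharge home, treat admission as a competing event and show cumulative incidence by arm in place of one minus Kaplan-Meier. Log-rank and Cox censored at admission may stay as the cause-specific comparison, read alongside disposition. If any-exit time is used, present it as emergency department length of stay and not as efficacy. Cost: wording and standard software. Disposition and length of stay are already recorded, but time from randomization to exit must be derivable. The cumulative-incidence display overlaps with disposition.

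3. **Statistical analysis plan, mixed models (minor).** Limit the repeated-measures time effect to PEFR/CAS, respiratory rate and heart rate. Compare albuterol hours and length of stay once per child, as the planned ANOVA already does. If a rank-sum test is preferred, write it in, because the plan currently says "Wilcoxon methods will be used to test for differences among categorical variables". Cost: one sentence.

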Baseline data: Once screened, consented, and enrolled, the following demographic data will be collected: birthdate, gender, race, time of arrival to the ED, details of any treatment by a referring provider, symptom type and duration (hours), time since last inhaled bronchodilator (minutes), time since systemic corticosteroids (minutes), number and type of inhaled bronchodilator treatments in the preceding 24 hours, all home medications, drug and food allergies, past medical history, number of hospital admissions for asthma over the prior 12 months, and number of ICU admissions over the child's lifetime. Initial temperature, respiratory rate, heart rate, blood pressure, and pulse oximetry will be recorded. Finally, height, PEFR, and CAS will be measured by the respiratory therapist (RT) immediately prior to the study intervention. Additionally, the subject's family will be asked to complete an Asthma Control Tool (ACT). The ACT is a measure of how well the participant's asthma has been controlled over the preceding three months.

Intervention: Subjects will then be randomly assigned (50% chance) to receive a weight based dose of IM epinephrine 1:1000 or no adjunctive medication. The dose will be 0.2 mg for subjects 20-30 kg and 0.3 mg for subjects greater than 30 kg. This will be injected intramuscularly by an ED nurse into the anterior thigh muscles of the subject using a 1 ml syringe and a 23 gauge one inch needle.

In addition to the study intervention, the standardized treatment pathway based on the current asthma guidelines in use at our center will be utilized. This pathway includes nebulized albuterol, ipratropium bromide, and systemic corticosteroids. The duration and dosages of these other interventions will be administered at the discretion of the treating provider.

Randomization: A block randomization scheme will be used to promote balance at the end of the study. Block randomization ensures that after each block of individuals are enrolled in the study (n individuals in total); an equal number of individuals will be assigned to each group (n/2 individuals in each group). We will use random block sizes of 8-12.

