Planned interim analysis: Interim analyses, reported to the data monitor will be performed at 6, 9 and 12 months after the first participant is randomized. A Lan-DeMets spending function approach will be used to monitor the need for early trial termination.

Power calculation: We will develop separate mixed-effects general linear models for each of the outcomes. For a sample size (n=54) the study has 81% power to detect a 12% main effect of each treatment for each outcome. The estimated power for detecting a 5% interaction effect is 32%. The total sample size required to achieve 80% power to detect an interaction effect, based on the full-factorial designed proposed, is n=1728; which is not a feasible number in which to recruit and enroll. In addition, we will develop Cox proportional hazards regression models to assess the association between group assignment and time related outcomes. For the anticipated sample size (n=54), this study has 80% power to detect a hazards ratio of 1.82 with two-sided α =0.05. Lastly, multiple logistic regression techniques will be utilized to assess

the association between group assignment and dichotomized outcomes. Using the dichotomized version of some outcomes, this study has 80% power to detect on odds ratio of 1.58 with a two sided α =0.05 (n=54). Therefore, we have more than sufficient numbers of participants in each comparison group.

We anticipate that less than 10% of all potential participants will drop out. Therefore, we will recruit a total of 60 individuals for the current study (n=30 per group). This is a feasible sample size for the research team to recruit and enroll in the current study. Power calculations were based on the anticipated total sample size (n=54) that will be available for complete analysis. Using a block randomization scheme (with random block sizes of 8-12), we anticipate that n=30 participants will be assigned to each group.

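### Read as one effect and one test, the 32% interaction power at n=54 and the n=1728 for 80% power do not agree, and the plan does not say which interaction either figure describes

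*Combined protocol and SAP*

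**What the plan says.** The Power calculation section opens with the main effect: "For a sample size (n=54) the study has 81% power to detect a 12% main effect of each treatment for each outcome". It then turns to interactions: "The estimated power for detecting a 5% interaction effect is 32" per cent. The next sentence reads: "The total sample size required to achieve 80% power to detect an interaction effect, based on the full-factorial designed proposed, is n=1728", and the section calls that number infeasible. The end of the section confirms the sample size behind these statements: "Power calculations were based on the anticipated total sample size (n=54) that will be available for complete analysis".

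The second interaction sentence does not repeat an effect size, and 5% is the only interaction size given anywhere. For these mixed-model figures the section gives no SD, within-child correlation, degrees of freedom or alpha. Two-sided 0.05 is stated only for the hazard ratio and the odds ratio.

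The Statistical analysis plan section sets arm as a fixed effect and time as a repeated-measures effect, brings in age, gender and ethnicity as covariates in secondary analyses, and proposes to examine every two-way interaction.

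**The concern.** Two adjacent sentences give a power at one sample size and a sample size for another power. For one effect and one test, either figure determines the other, so the pair can be checked although the plan gives no SD. It fails the check by a wide margin.

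What is at stake is how a null interaction result would be read. This section is the plan's only statement of what the interaction tests can detect. At 32% power, a real 5% interaction would be found about one time in three. At 7 to 8%, the test would reject hardly more often than its assumed 5% error rate. The 1728 figure is also the plan's stated reason for calling adequate interaction power out of reach.

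**Working it through.** **Inputs from the documents**
- Analysed sample size 54, with 32% power for a 5% interaction (Power calculation).
- Total of 1728 for 80% power (Power calculation).
- Equal allocation (Intervention).

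**Assumptions**
- Two-sided alpha of 0.05, carried over from the hazard-ratio and odds-ratio statements.
- Both sentences concern the same effect and the same test.

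**Reproducing the plan's figures.** With no SD, neither 32% nor 1728 can be rebuilt from raw inputs. Only the pair can be tested. For a fixed effect and test, the noncentrality grows with the square root of N. SD, within-child correlation and number of visits are the same at both sample sizes, so they cancel.

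**Forward, taking 32% at 54 as right**
- Noncentrality at 54: z(0.975) + z(0.32) = 1.960 − 0.468 = 1.492.
- Noncentrality for 80% power: 1.960 + 0.842 = 2.802.
- N for 80% power: 54 × (2.802 / 1.492)² = about 190.
- At N = 1728 the noncentrality would be 1.492 × √(1728/54) = 1.492 × √32 = 8.44, which is power above 99.99%.

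**Reverse, taking 1728 as right for the 5% effect**
- Noncentrality at 54: 2.802 / √32 = 0.495.
- Power at 54: Φ(0.495 − 1.960) = 7.2%, or about 7.9% counting both tails.

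**Sensitivity to the form of the test and to alpha**

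| Test | N for 80%, if 32% at 54 is right | Power at 54, if 1728 is right |
|---|---|---|
| Normal, two-sided 0.05 | 190 | 7.9% |
| F, 1 df, alpha 0.05 | 185 | 7.8% |
| F, 4 df (arm × time), alpha 0.05 | 159 | 6.9% |
| F, 5 df (arm × time), alpha 0.05 | 155 | 6.8% |
| Normal, two-sided 0.10 | 241 | 13.3% |
| Normal, two-sided 0.20 | 368 | 23.1% |

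Under the normal approximation the two stated figures agree only at a two-sided alpha of about 0.45.

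**What would let both stand.** If 32% for 5% is right and the test is unchanged, 80% power at 1728 corresponds to an interaction of 5 × (2.802 / 1.492) / √32 = about 1.7%. No such effect is stated.

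**The case against.** The strongest reply is that the two sentences need not describe the same thing. The second drops the 5%, speaks only of an interaction effect, and adds a reference to a full-factorial design. The Statistical analysis plan section allows at least two kinds of interaction: arm by time, estimated within children, and arm by a covariate such as age or gender, estimated between children. Their standard errors can differ greatly. Suppose an SD of about 15.25 is back-solved from the 81% power for a 12% main effect. A 5% arm-by-time contrast between two visits then reaches 32% power at 54 if the within-child correlation is about 0.67. A 5% arm-by-binary-covariate interaction needs about 1,391 children if the covariate splits 30/70 and about 1,825 if it splits 20/80, so a split in between gives 1728.

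This stands as far as it goes: it shows that the figures could coexist. It does not show that the sponsor calculated them this way. The SD, correlation and split are all assumed, and the reconciliation needs a change of interaction between adjacent sentences that nothing announces. Nor does the full-factorial wording identify a second test: "Subjects will then be randomly assigned (50% chance) to receive a weight based dose of IM epinephrine 1:1000 or no adjunctive medication" describes a two-arm comparison. On this reading the 1728 still has no stated effect or test and cannot be interpreted.

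A second reply is that little depends on the figures. That is largely right. Even 190 analysed children, at the three to five per month in the Recruitment plan, would take 38 to 63 months (190/5 and 190/3) before any dropout, against the 12 to 20 planned. The plan already presents interactions as underpowered, and they remain so.

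**Conclusion.** The pair is inconsistent on its natural reading, by about nine-fold in sample size (1728/190 = 9.1) or four-fold in power (32% against about 8%). This rests on one effect, one test and two-sided 0.05. It does not depend on the SD, the within-child correlation or the number of visits.

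Three stronger readings are tempting, and the documents do not support them:
- **That one figure must be wrong.** This holds only if both sentences mean the same effect and test. The plan does not say so outright, and it does not show which figure would be at fault. That 1728 equals 32 × 54 proves no slip.
- **That the correct figures are about 9% power and about 1,170 children.** These follow from the SD back-solved through a simple two-sample comparison and from a covariate assumed to split evenly. The plan states neither, and uses mixed models.
- **That the trial's size is undermined.** The 54 analysed, the 60 enrolled and the primary comparison do not depend on either interaction figure.

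Severity is minor: a clear, easily corrected inconsistency in secondary planning figures.

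**What to change.** Re-run the interaction calculation and state one consistent pair for a single named interaction: arm by time, or arm by a named covariate. Give the effect size and its units, the SD, the within-child correlation, the degrees of freedom and the alpha. Then:
- If 32% at 54 is reproduced, replace 1728 with the matching total, about 190 for a 1-df test at two-sided 0.05.
- If 1728 is reproduced for the 5% effect, replace 32% with about 8%.
- If the two figures were meant for different interactions, say so and define each.
- Delete any figure that cannot be reproduced, and do not substitute one built on an assumed SD or covariate split.

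The cost is one corrected sentence in the Power calculation section, and the stated interaction power may become less favourable. Enrolment does not change.

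### With 54 children, power is at most about 14% for an odds ratio of 1.58 and about 60% for a hazard ratio of 1.82, not the 80% stated for each

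*Combined protocol and SAP*

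**What the plan says.** The Power calculation section makes three claims of adequate power at n=54. For the mixed models, "the study has 81% power to detect a 12% main effect of each treatment for each outcome". For the survival models, "For the anticipated sample size (n=54), this study has 80% power to detect a hazards ratio of 1.82". For the logistic models, "this study has 80% power to detect on odds ratio of 1.58". The last two are both given at two-sided alpha 0.05. The section then concludes: "Therefore, we have more than sufficient numbers of participants in each comparison group".

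The same section fixes what the hazard ratio and odds ratio refer to. The survival analysis uses "Cox proportional hazards regression models to assess the association between group assignment and time related outcomes", and the logistic analysis assesses "the association between group assignment and dichotomized outcomes". It also settles that 54 is a total and not a per-arm figure: "Power calculations were based on the anticipated total sample size (n=54) that will be available for complete analysis". Recruitment is 60, split 30 and 30, with dropout below 10%. No outcome rate and no event count is given.

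The Statistical analysis plan says where these models apply. For the binary outcomes, "logistic regression techniques will also be used to evaluate (7) need for supplemental oxygen and (8) need for albuterol". Kaplan-Meier, log-rank and Cox methods are planned for time-related variables, with time to discharge as the example.

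**The concern.** An odds ratio of 1.58 is a modest effect. At its most favourable it separates rates of about 44% and 56%, which is roughly 12 against 15 children out of 27. A two-arm trial of this size cannot reliably detect a difference of three children. The hazard ratio claim has a simpler problem: the usual formulas ask for more events than there are children.

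The practical risk lies in how a null secondary result is read. A reader told that the trial had 80% power at an odds ratio of 1.58 could take non-significance for need for oxygen or albuterol as evidence of no effect. As an illustration, 12/27 events in each arm gives an observed odds ratio of 1.0. The standard error of the log odds ratio is √[2(1/12 + 1/15)] = 0.548, so the 95% confidence interval is about 0.34 to 2.93. That interval contains both 1/1.58 = 0.63 and 1.58.

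**Working it through.** **Inputs.** From the Power calculation section: 54 analysed, 1:1 allocation, hence 27 per arm; group assignment as a binary predictor; two-sided alpha 0.05 (z = 1.960); 80% power (z = 0.842). The plan gives no outcome rate or event count, so the checks below are upper bounds. The odds ratio is evaluated at every control rate and the best result kept; the hazard ratio is evaluated with every analysed child having the event.

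**Odds ratio 1.58.** Pooled two-proportion formula: power = Φ{[|p1 − p0| − 1.960·√(2p̄(1 − p̄)/27)] / √[(p0(1 − p0) + p1(1 − p1))/27]}.

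- Power is greatest at p0 = 0.445, where an odds ratio of 1.58 gives p1 = 0.559 and a difference of 0.114.
- The two standard errors are 0.1361 (pooled) and 0.1352 (unpooled).
- Power = Φ[(0.1139 − 1.960 × 0.1361)/0.1352] = Φ(−1.13) = 0.129.
- For a reduction (odds ratio 1/1.58), the mirror case p0 = 0.555, p1 = 0.441 gives the same result.
- Over control rates from 5% to 95%, power runs from 5% to 13%.

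Other methods, each at its most favourable control rate:

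| Method, 27 per arm | Maximum power |
|---|---|
| Pooled two-proportion | 12.9% |
| Unpooled two-proportion | 13.2% |
| Wald test of log odds ratio | 13.0% |
| Logistic likelihood-ratio test, exact enumeration | 13.8% |
| Fisher's exact test | 7.8% |

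The total needed for 80% power is 604 (pooled), 598 (unpooled) or 610 (Wald). The first is 604/54 = 11.2 times the planned analysis set.

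**Hazard ratio 1.82.** ln(1.82) = 0.599.

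- Events needed, Schoenfeld: 4(1.960 + 0.842)²/0.599² = 87.5, so 88.
- Events needed, Freedman: (1.960 + 0.842)² × (2.82/0.82)² = 92.8, so 93.
- Power with 54 events, Schoenfeld: Φ(√54/2 × 0.599 − 1.960) = Φ(0.240) = 59.5%.
- Power with 54 events, Freedman: Φ(√54 × 0.82/2.82 − 1.960) = Φ(0.177) = 57.0%.
- Simulated log-rank test, 27 per arm, all with events, 20,000 runs: 56.9%.
- With fewer events, Schoenfeld power falls: 54.6% at 48, 47.4% at 40, 37.5% at 30.

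**Attempts to recover the stated 80%.**

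| Alternative reading | OR 1.58, maximum power | HR 1.82, maximum power (Schoenfeld) |
|---|---|---|
| All 60 analysed | 14% | 64% |
| One-sided test | 21% | 71% |
| 54 per arm | 22% | 87.5% (108 events) |
| Three time points treated as independent | about 30% to 31% | – |
| Five time points treated as independent | 46% | – |
| Continuous predictor, effect per SD | 39% | – |

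None gives 80%. Only the 54-per-arm reading takes the hazard ratio above 80%, and it contradicts the stated total.

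**What 54 children can detect with 80% power.**

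- *Odds ratio, pooled formula.* The best case for a reduction is 69% against about 32%: (0.317/0.683)/(0.69/0.31) = 0.21 = 1/4.8. The best case for an increase is 4.8, at a control rate near 31%. Elsewhere the effect must be more extreme. For a reduction it is 1/5.1 at a control rate of 80%, 1/6.8 at 90%, 1/5.6 at 50% and 1/14.6 at 31%.
- *Odds ratio, other formulas.* The best case is 4.4 (unpooled) or 5.2 (Wald).
- *Hazard ratio, 54 events.* Schoenfeld: exp[2(1.960 + 0.842)/√54] = 2.14. Freedman: with r = 2.802/√54 = 0.381, (1 + r)/(1 − r) = 2.23. Simulated log-rank power is 76% at 2.14 and 81% at 2.23.

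**The case against.** The strongest defence is that the plan gives no outcome rates or event counts, so its 80% cannot be tested. That fails because the figures above are maxima over all rates and event counts. Repeated readings at 60, 90 and 120 minutes could add information, but the plan does not invoke them for this power figure, and even treating them as independent leaves power near 31%.

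A second objection is that the impact is limited, and this stands. The primary outcome is the 15-minute change in PEFR/CAS, analysed by a mixed model. Only secondary analyses are affected. ED length of stay and hours of albuterol also have mixed models, and the two need-for-treatment outcomes are also assigned negative binomial regression. Nothing in the plan says a null secondary result will be read as no effect; that risk is an inference.

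Third, the Fisher figure of 7.8% is not a direct test of the claim, since the odds ratio is tied to logistic regression. That is fair: the 13% to 14% figures are the relevant ones.

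Fourth, the replacement values depend on the formula. At an odds ratio of 1/4.8 with a 69% control rate, power is 79% by the likelihood-ratio test but 69% by Fisher's test, which would need an odds ratio of about 5.9 in its best case. The log-rank simulation favours 2.23 over 2.14. The corrected text should therefore name its formula and call the values approximate.

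**Conclusion.** Both statements are wrong as written. Stated power is 80% in each case. Attainable power is at most about 14% for the odds ratio of 1.58 and about 60% for the hazard ratio of 1.82. The conclusion rests on the plan's own terms (54 in total, equal allocation, treatment group as predictor, two-sided 0.05) and on assumptions chosen in the plan's favour: the best possible control rate, and an event in every child. Real event rates can only lower these figures. The choice of formula moves the results by a few points at most, against shortfalls of about 66 and 20 points.

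The claim of more than sufficient numbers is thus unsupported for the binary and time-to-event secondary outcomes at these effect sizes. The 81% mixed-model statement was not assessed here. This should be corrected, but it does not undermine the primary analysis.

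**What to change.** Keep the recruitment target of 60 and replace the hazard ratio and odds ratio sentences in the Power calculation section with wording such as:

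> With n=54 (27 per arm, two-sided alpha 0.05, pooled two-proportion formula), the study has 80% power at best for an odds ratio of about 4.8 for an increase in events (control rate near 31%) or about 1/4.8 = 0.21 for a decrease (control rate near 69%); more extreme odds ratios are needed at other control rates. If every child has the event, it has 80% power for a hazard ratio of about 2.14 (Schoenfeld) or 2.23 (Freedman); a larger hazard ratio is needed if fewer do.

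If only one hazard ratio is given, 2.23 is the safer choice because it agrees better with the simulated log-rank test. In addition:

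- State the assumed event rate for each binary and time-to-event outcome.
- Limit the sufficient-numbers sentence to the mixed-model main effect, or delete it.
- Describe the binary and time-to-event secondary analyses as low-powered, and report them with confidence intervals.

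The cost is one reworded paragraph. No patients are added, and the design, conduct, tests and primary analysis do not change. The only downside is that the stated secondary power looks less favourable.
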